 Email: [contact]

A5. Funding Source:

Baylor College of Medicine (Internal Funding Only)

A6a. Institution(s) where work will be performed:

TCH: Texas Children's Hospital

A6b. Research conducted outside of the United States:

Country:
 Facility/Institution:
 Contact/Investigator:
 Phone Number:

If documentation of assurances has not been sent to the Office of Research, please explain:

A7. Research Category:

A8. Therapeutic Intent

Does this trial have therapeutic intent?

No

A9. ClinicalTrials.gov Registration

Does this protocol/trial require registration on ClinicalTrials.gov due to it: meeting the definition of an Applicable Clinical Trial, being required under the terms and conditions of an award, or being proposed to be published in ICMJE journals?

Yes

Who will be responsible for registering and maintaining the registration of this Applicable Clinical Trial?

The BCM PI will register the trial because either:

- the trial is BCM PI-initiated,
- BCM is the lead site of this multicenter trial, or,

- the industry sponsor has instructed the BCM PI to register the trial, or,
- registration of this trial is required as a term and condition of the reward by the funding agency.

ClinicalTrials.gov Identifier:
NCT02206685

Section B: Exempt Request

B. Exempt From IRB Review

Not Applicable

Section C: Background Information

Scoliosis is a disease that involves lateral and/or rotational deformity of the spine and can affect up to 4% of the population. Typically, surgery is considered when Cobb's angle, which is a measurement used for evaluation of curves in scoliosis on an anterior-posterior radiographic projection of the spine, is greater than 50 degrees in the thoracic region (40 degrees in the lumbar region) or when the curvature causes significant pain, or respiratory and cardiovascular restriction. Patient undergoing this surgical correction experience severe pain in the postoperative period and the management includes the use of opioid-based patient-controlled analgesia (PCA).

Methadone is an opioid with one of the longest elimination half-life and has been used as an effective analgesic for acute, chronic, neuropathic, and cancer pain in adults, children, and even neonates¹⁻⁵. Its long duration of action and antagonism to the N-methyl-d-aspartate receptor may decrease the need for PCA use in the postoperative period. Gourlay² demonstrated the effectiveness and utility of perioperative methadone including the advantages of longer analgesia with no serious side effects of respiratory depression. A recent study by Gottschalk² in adult patients demonstrated a 50% reduction of postoperative opioids at 48 hours and lower pain scores after a single bolus of methadone before surgical incision. However, a major weakness of the study is that patients did not receive equipotent intraoperative opioids. In addition, the adolescent patient population will undergo a much larger surgical incision with potential for greater postoperative pain. Despite this potential benefit, methadone is seldom used in the perioperative setting. A more recent pharmacokinetic study of methadone in adolescents undergoing spine surgery failed to show a reduction in opioid consumption as it was powered to determine pharmacokinetics and not a secondary endpoint of postoperative opioid consumption. An appropriately powered study is still required to determine the efficacy of methadone in reducing postoperative pain after spine surgery.

1. Nicholson AB. Methadone for cancer pain. *Cochrane Database Syst Rev* 2007:CD003971 2. Gourlay GK et al. Pharmacodynamics and pharmacokinetics of methadone during perioperative period. *Anesthesiology* 1982; 57:458-67. 3. Gottschalk A et al. Intraoperative methadone improves postoperative pain control in patients undergoing complex spine surgery. *Anesth Analg* 2011; 112:218-23. 4. Sharma A, Tallchief D, Blood J, Kim T, London A, Kharasch ED: Perioperative pharmacokinetics of methadone in adolescents. *Anesthesiology* 2011; 115:1153-61. 5. Berde CB, Beyer JE, Bournaki MC, Levin CR, Sethna NF: Comparison of morphine and methadone for prevention of postoperative pain in 3- to 7-year-old children. *J Pediatr* 1991; 119:136-41

Section D: Purpose and Objectives

The aim of this study is to explore the efficacy of a single intra-operative dose of methadone in patients with idiopathic scoliosis undergoing multi-level posterior instrumentation and spinal fusion. The primary endpoints is the total opioid usage during POD (postoperative day) 0-4. Secondary endpoints include and pain scores during rest and with activity (getting out bed and ambulation) on POD 0-5 and side effects of pain medications

Section E: Protocol Risks/Subjects

E1. Risk Category

Category 2: Research involving greater than minimal risk, but presenting the prospect of direct benefit to the individual subjects.

E2. Subjects

Gender:
Both

Age:

Adolescent (13-17 yrs), Child (3-12 yrs)

Ethnicity:

All Ethnicities

Primary Language:

English, Spanish

Groups to be recruited will include:

Patients

Which if any of the following vulnerable populations will be recruited as subjects?

Children

Vulnerable populations require special protections. How will you obtain informed consent, protect subject confidentiality, and prevent undue coercion?

Patients presenting for spinal surgery will be identified from the Texas Children's Hospital operating room schedule that is routinely available to pediatric anesthesiologists. This will be cross referenced with the pediatric orthopedic surgeons' operative schedule as these cases are scheduled weeks to months in advance. The chart is reviewed to insure that the patient qualifies based on the inclusion and exclusion criteria.

Potential subjects will be approached about participation on their visit to our preoperative screening clinic which occurs a few days prior to surgery. The child will be approached with parental presence during the preoperative screening visit and age appropriate language will be used to explain the study and answer any questions. Every opportunity will be given to answering questions and discussing their options throughout the study. Enrollment in the study will only occur if the child assents and the parent consent. Voluntary participation will be emphasized during recruitment of patients. A copy of the IRB approved written consent form will be given to parents with time allowed for reading and considering enrollment. Another opportunity to raise questions will be presented on the day of surgery in the holding area. All questions will be fully answered and the child will then be asked to sign their name on the assent portion with parent or guardian signing the IRB approved consent. A translator will be available for Spanish speakers and a fully translated consent form approved by the IRB will be used for these subjects. (A Spanish consent will be submitted as an amendment after the English consent is approved. No Spanish speakers will be recruited for enrollment prior to IRB approval of a Spanish translation of the consent form.) Participants will be assured that every effort will be made to protect privacy and to prevent a breach of confidentiality.

E3. Pregnant woman/fetus

Will pregnant women and/or fetuses (as described in 45 CFR 46 Subpart B) be enrolled in the research?

No

E4. Neonates

Will neonates of uncertain viability or nonviable neonates (as described in 45 CFR 46 Subpart B) be enrolled in the research?

No

E5. Children

Will children be enrolled in the research?

Yes

Section F: Design/Procedure**F1. Design**

Select one category that most adequately describes your research:

y) Drug, Phase IV, Single Center

Discuss the research design including but not limited to such issues as: probability of group assignment, potential for subject to be randomized to placebo group, use of control subjects, etc.

This patient and observer blinded prospective randomized study will be performed on patients (aged 10 - 17years, both males and females, from all ethnic backgrounds) undergoing multilevel thoraco-lumbar spine surgery with instrumentation and fusion at Texas Children's Hospital, Houston, TX. After obtaining IRB (Institutional Review Board) approval and written informed consent from each patient or his or her legal representative, 56 patients scheduled for multilevel thoraco-lumbar spine surgery with instrumentation and fusion will randomly be assigned into two groups (control or treatment group) based on a computer generated random number using Random Allocation Software For Parallel Group Randomized Trials. There is an equal chance of being assigned to either group. The control group will be given placebo; whereas the treatment group will receive methadone 0.2 mg/kg intravenously.

Inclusion Criteria:

- 1) Patient age 10 \geq 17 years
- 2) Patients undergoing multilevel thoraco-lumbar spine surgery with instrumentation and fusion

Exclusion Criteria:

- 1) Preoperative methadone therapy
- 2) Inability to use the PCA
- 3) Allergy to methadone or morphine
- 4) Morbid obesity with a body mass index >36.0 kg/m²
- 5) Patients with chronic renal failure defined by serum creatinine >2.0 mg/dL
- 6) Liver failure defined as a history of cirrhosis or fulminant hepatic failure
- 7) Preoperative congenital heart disease or arrhythmias
- 8) Patient refusal to participate in study
- 9) Pregnancy (It is standard of care for all post menarche female patients to undergo a urine pregnancy test prior to surgery).

F2. Procedure

The perioperative management of patients will be in keeping with the current standard practices at Texas Children's Hospital. Before surgery, patients will be asked to rate their baseline pain using a verbal rating scale from 1 to 10 by a member of the research team. In addition, information on preoperative opioid consumption during the last 30 days will be collected.

Muscle spasms after scoliosis surgery are a common cause of postoperative pain. Our current practice is to provide oral or IV diazepam to treat muscle spasms. Many patients who undergo scoliosis repair receive pre-operatively oral diazepam or midazolam for anxiolysis. In order to prevent introducing a confounding factor in the evaluation of postoperative pain scores in the recovery period, the protocol will require all patients to receive the same preoperative medication (oral diazepam). After intravenous access, endotracheal intubation will be facilitated with additional bolus of propofol 1-3 mg/kg or succinylcholine 1-2 mg/kg at the discretion of the intra-operative anesthesiologist. According to the randomization plan, after intubation, the control group will receive a 20 ml normal saline placebo infusion over 10 minutes, while the treatment group will receive 0.2 mg/kg methadone diluted to a 20 ml infusion over 10 minutes. The inhalational agent will be turned off at intubation in keeping with standard TCH practices. Total intravenous anesthesia in both groups will be maintained in keeping with standard TCH practices for neuromonitoring (somatosensory evoked potentials (SSEPs) and motor evoked potentials (MEPs) with propofol 75 - 200 mcg/kg/min and sufentanil 0.2 \geq 0.5 mcg/kg/hour, adjusting the doses to achieve a targeted bispectral index level of 40-60. Nicardipine infusion may be used for controlled hypotension at the discretion of the intra-operative anesthesiologist. The sufentanil and propofol infusion will be turned off when the second rod is placed and after the final SSEPs, MEPs are obtained. Anesthesia will be maintained with inhalational agent until the end of the surgical procedure. At the end of surgical procedure, residual neuromuscular blockade will be antagonized and the trachea extubated in the operating room when the Anesthesiologist decides it is safe. The patient will then be transferred to the post anesthesia recovery room (PACU). Both the intra-operative anesthesiologist and the researcher staff gathering the PACU pain scores and use of PCA will be blinded to the medication.

Postoperative Analgesia All groups: In keeping with current practice, supplemental oxygen will be available for oxygen saturations less than 94% during spontaneous ventilation. All patients will be monitored with continuous pulse oximetry as in keeping with practice at TCH. Every patient will have a patient controlled analgesia (PCA) morphine pump with a basal rate infusion of 0.01 mg/kg/hour, a demand dose 0.02 mg/kg with a lockout time of 10 minutes to be started in the PACU once the patient emerges from the anesthetic. The patient will be administered diazepam 0.05 mg/kg IV or oral with maximum of 5 mg every 6 hours as needed for muscle spasms in keeping with current practice. On POD 1, the basal rate of morphine will be discontinued and ketorolac 0.5 mg/kg every 6 hours initiated in keeping with current practices. On POD 3, the patient will be transitioned from the PCA with scheduled oral hydrocodone/acetaminophen at a dosage of 0.135 mg/kg of hydrocodone with a maximum of 15 mg every 4 hours in keeping with current practice. The PCA will be available for use during the transition for breakthrough pain.

Postoperatively, patients will be asked to rate their pain using a validated pain scale (a verbal rating scale where 0 = no pain and 10 = worse pain ever) by a blinded research staff member. These pain scores will be collected at 1 hour after entry into recovery and every 4 hours during the first five days of hospitalization both at rest and during activity by the nurses. The cumulative intravenous opioid requirement at 24, 48, and 72 hour will be recorded. The cumulative breakthrough intravenous opioid requirement after initiation of oral pain medication will also be collected. The level of sedation will be determined using the University of Michigan Sedation Scale. In addition, complications such as the incidence of hypotension (defined as mean arterial blood pressure less than 50 mm Hg), the need for vasopressors, the incidence of respiratory depression (defined as a respiratory rate less than 8 breaths per minute, respiratory arrest, or the need for naloxone), the incidence of hypoxemia or desaturation (defined as oxygen saturation [Sao₂] less than 90% or the need for a supplemental oxygen to maintain Sao₂ greater than 94%), the incidence of cardiac arrhythmias, and the incidence of nausea and vomiting including the treatment of side effects will be also recorded. Upon discharge from the hospital, the patients will be asked to keep a diary consisting of daily opioid usage, episodes of nausea and vomiting, daily activity level, and satisfaction scores. As part of standard routine post-surgical followup in the orthopedic clinic, information is collected from the patients which consist of questionnaires regarding pain scores, functional status, activity level, and quality of life. The research team will collect this information at 3 months and 6 months postoperatively.

Section G: Sample Size/Data Analysis**G1. Sample Size**

How many subjects (or specimens, or charts) will be used in this study?

Local: 98

Worldwide: 98

Please indicate why you chose the sample size proposed:

The sample size was based on the assumption that opioid use in the first 3 days in the placebo group would be similar to that in a previously published study of the same patient population undergoing spine surgery (mean 275 mg SD 75 mg). A group size of 28 would be required for an 80% power of detecting a 30% reduction in opioid use from 275 to 200 mg at the 0.05 level of significance. Allowing for a 50% dropout rate for incomplete data, we will recruit 49 patients in each group for a total of 98 subjects.

G2. Data Analysis

Provide a description of your plan for data analysis. State the types of comparisons you plan (e.g. comparison of means, comparison of proportions, regressions, analysis of variance). Which is the PRIMARY comparison/analysis? How will the analyses proposed relate to the primary purposes of your study?

The primary endpoint of the study is the morphine consumption during the first 72 postoperative hours. The secondary outcomes include pain scores and the incidence of side effects such as respiratory depression, nausea, and vomiting. Continuous data including pain scores will be first examined for a normal distribution by the Shapiro χ Wilk test. The outcome variables between the two groups will be compared with Student's t -test where appropriate, for normally distributed continuous data or by nonparametric tests if the data were not normally distributed. It is anticipated that the distribution of pain scores will not be normal and that non-parametric tests will be required. Categorical data including patient gender, ASA physical status, incidence of side effects (respiratory depression, need for oxygen beyond the first 2 hours, nausea and vomiting) will be compared by Fisher's exact test. Analysis of variance for repeated measures will be performed to compare differences in pain scores between the treatment groups with time. Data will be presented as mean, standard deviation, median values or numbers (percentages). P values less than 0.05 will be considered statistically significant. In order to maintain a robust statistical analysis, we will also examine the differences in subjects with and without completely evaluable data in known factors that affect postoperative pain after spine surgery (e.g., age, gender, ASA physical status, duration of surgery, intraoperative opioids medications, time of the PACU stay, mean and peak pain scores and recorded opioid consumption in the PACU before discharge). Failure to show a difference in these factors may suggest that the missing data can be considered to be missing at random.

Section H: Potential Risks/Discomforts

H1. Potential Risks/Discomforts

Describe and assess any potential risks/discomforts; (physical, psychological, social, legal, or other) and assess the likelihood and seriousness of such risks:

In this study, we are comparing the addition of another opioid pain medication to reduce pain scores and overall total hospital opioid consumption. Current standard practices for patients undergoing multi-level spine surgery will be used with the exception of methadone given to the treatment group. Methadone may induce prolongation of the rate-corrected QT interval (QTc); however, patients with cardiac arrhythmias or congenital heart disease will be excluded from the study. Side effects of respiratory depression from methadone should not be greater than with typical morphine usage.

Additional risks of the study are the small chance of loss of privacy. The data will be coded. No data identifying the patient will be extracted from the medical records and all data will be kept locked in the offices of the Principal Investigator. Any electronic version will be kept in a password protected network servers controlled by the IT services at the TCH. Computers with access to this network are kept in a locked office where entry is limited to those with an ID key card. This office is located inside the office of the Department of Anesthesiology at Texas Children's Hospital. Unauthorized individuals would not be able to enter these facilities. The likelihood of such events is minimal.

H2. Data and safety monitoring plan

Do the study activities impart greater than minimal risk to subjects?

Yes

NOTE: The answer to the questions in H2 requires the completion of the form: 'Section H – Data and Safety Monitoring Plan' as an attachment in Section S.

H3. Coordination of information among sites for multi-site research

Is the BCM Principal Investigator acting as the SPONSOR-INVESTIGATOR for this multi-site research?

No or Not Applicable

Is BCM the COORDINATING CENTER for this multi-site research?

No or Not Applicable

Section I: Potential Benefits

Describe potential benefit(s) to be gained by the individual subject as a result of participating in the planned work.

Patients assigned to the methadone group may have reduced postoperative pain scores and a reduction of total consumption of postoperative opioids. Patients with less opioid use may benefit from fewer side effects. However, it is possible that there will be no benefits from participating in the study.

Describe potential benefit(s) to society of the planned work.

Data from this study can be used to determine if methadone provides better pain control in the perioperative setting. Knowledge obtained from this study may allow anesthesiologists from other institutions caring for children and adolescents undergoing similar painful procedures to use this medication to reduce pain.

Do anticipated benefits outweigh potential risks? Discuss the risk-to-benefit ratio.

The risks in this study do not vary from the risks of standard practices at TCH for children undergoing multi-level thoracolumbar spinal instrumentation and fusion. The additional minor risk of an unlikely loss of privacy is outweighed by the societal benefits from this knowledge.

Section J: Consent Procedures

J1. Waiver of Consent

Will any portion of this research require a waiver of consent and authorization?

No

J1a. Waiver of requirement for written documentation of Consent

Will this research require a waiver of the requirement for written documentation of informed consent?

No

J2. Consent Procedures

Who will recruit subjects for this study?

PI
PI's staff

Describe how research population will be identified, recruitment procedures, any waiting period between informing the prospective participant and obtaining consent, steps taken to minimize the possibility of coercion or undue influence and consent procedures in detail.

Patients presenting for spinal surgery will be identified from the Texas Children's Hospital operating room schedule that is routinely available to pediatric anesthesiologists. This will be cross referenced with the pediatric orthopedic surgeons' operative schedule as these cases are scheduled weeks to months in advance. The chart is reviewed to insure that the patient qualifies based on the inclusion and exclusion criteria. The study staff will ask the surgeon if they may approach the patient and parents about the study.

Potential subjects will be approached about participation on their visit to our preoperative screening clinic which occurs a few days prior to surgery. The child will be approached with parental presence during the preoperative screening visit and age appropriate language will be used to explain the study and answer any questions. Every opportunity will be given to answering questions and discussing their options throughout the study. Enrollment in the study will only occur if the child assents and the parent consent. Voluntary participation will be emphasized during recruitment of patients. A copy of the IRB approved written consent form will be given to parents with time allowed for reading and considering enrollment. Another opportunity to raise questions will be presented on the day of surgery in the holding area. All questions will be fully answered and the child will then be asked to sign their name on the assent portion with parent signing consent. A copy of the signed consent form will be given to parents.

A TCH translator or a Spanish-speaking research staff will thoroughly explain the study to the child and the parent. After all questions are answered and the study staff is assured that the study is understood and participation is agreed, the child will sign their name on the assent portion parent signing consent. A copy of the consent will be given to the parent.

Are foreign language consent forms required for this protocol?

Yes

Which of the following ways will you document informed consent in languages other than English?

A full-length informed consent document

J3. Privacy and Intrusiveness

Will the research involve observation or intrusion in situations where the subjects would normally have an expectation of privacy?

Yes

J4. Children

Will children be enrolled in the research?

Yes

J5. Neonates

Will non-viable neonates or neonates of uncertain viability be involved in research?

No

J6. Consent Capacity - Adults who lack capacity

Will Adult subjects who lack the capacity to give informed consent be enrolled in the research?

No

J7. Prisoners

Will Prisoners be enrolled in the research?

No

Section K: Research Related Health Information and Confidentiality

Will research data include identifiable subject information?

Yes

Information from health records such as diagnoses, progress notes, medications, lab or radiology findings, etc.

Yes

Specific information concerning alcohol abuse:

No

Specific information concerning drug abuse:

No

Specific information concerning sickle cell anemia:

No

Specific information concerning HIV:

No

Specific information concerning psychiatry notes:

No

Demographic information (name, D.O.B., age, gender, race, etc.):

Yes

Full Social Security #:

No

Partial Social Security # (Last four digits):

No

Billing or financial records:

No

Photographs, videotapes, and/or audiotapes of you:

No

Other:

No

At what institution will the physical research data be kept?

Texas Children's Hospital

How will such physical research data be secured?

PHI data is currently stored in a locked drawer in the PI's research office at the department of Anesthesiology located at Texas Children's Hospital. The entrance to the department is always locked and accessible only to research personnel using key cards and regularly patrolled by security every day.

At what institution will the electronic research data be kept?

All computerized electronic data is kept in a password protected network servers controlled by Information Technology services at Texas Children's Hospital. Computers with access to this network are located in the PI's research office where access is limited by personal ID card entry. Computers are locked and must be accessed with using personal password.

Such electronic research data will be secured via BCM IT Services- provided secured network storage of electronic research data (Non-Portable devices only):

No

Such electronic research data will be secured via Other:

Yes, (describe below):

Texas Children's IT services with secured network servers. No portable devices are being used to store any data.

Will there be anyone besides the PI, the study staff, the IRB and the sponsor, who will have access to identifiable research data?

No

Please describe the methods of transmission of any research data (including PHI, sensitive, and non-sensitive data) to sponsors and/or collaborators.

No protected health information or data will be transmitted to any sponsors or collaborators.

Will you obtain a Certificate of Confidentiality for this study?

No

Please further discuss any potential confidentiality issues related to this study.

Study findings may be published at professional meetings and/or peer reviewed journals. No data identifying an individual patient will be included in any report of the study.

Section L: Cost/Payment

Delineate clinical procedures from research procedures. Will subject's insurance (or subject) be responsible for research related costs? If so state for which items subject's insurance (or subject) will be responsible (surgery, device, drugs, etc). If appropriate, discuss the availability of financial counseling.

Patient will be responsible for costs of anesthesia and analgesia, regardless of study enrollment. There is no additional cost to the patient for participation in the study.

If subjects will be paid (money, gift certificates, coupons, etc.) to participate in this research project, please note the total dollar amount (or dollar value amount) and distribution plan (one payment, pro-rated payment, paid upon completion, etc) of the payment.

Dollar Amount:

0

Distribution Plan:

Section M: Genetics

How would you classify your genetic study?

Discuss the potential for psychological, social, and/or physical harm subsequent to participation in this research. Please discuss, considering the following areas: risks to privacy, confidentiality, insurability, employability, immigration status, paternity status, educational opportunities, or social stigma.

Will subjects be offered any type of genetic education or counseling, and if so, who will provide the education or counseling and under what conditions will it be provided? If there is the possibility that a family's pedigree will be presented or published, please describe how you will protect family member's confidentiality?

Section N: Sample Collection

None

Section O: Drug Studies

Does the research involve the use of ANY drug* or biologic? (*A drug is defined as any substance that is used to elicit a pharmacologic or physiologic response whether it is for treatment or diagnostic purposes)

No

Does the research involve the use of ANY gene transfer agent for human gene transfer research?

No

O1. Current Drugs

Is this study placebo-controlled?

Yes

If yes, be sure that you justify the use of the placebo for this research in the space below.

An appropriately powered study is still required to determine the efficacy of methadone in reducing postoperative pain after spine surgery and must be compared against a placebo to obtain.

Will the research involve a radioactive drug?

No

Section P: Device Studies

Does this research study involve the use of ANY device?

No

Section Q. Consent Form(s)

None

Section R: Advertisements

None

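### The primary endpoint is defined in two ways: total opioid over POD 0-4 in Section D, morphine over the first 72 postoperative hours in Section G2

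*Combined protocol and SAP*

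**What the plan says.** Section D, the statement of purpose and objectives, gives the endpoint as: "The primary endpoints is the total opioid usage during POD (postoperative day) 0-4".

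Section G2 answers the form's question "Which is the PRIMARY comparison/analysis" with: "The primary endpoint of the study is the morphine consumption during the first 72 postoperative hours".

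The other sections that bear on it are:

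- **G1 (sample size).** The trial is sized on "opioid use in the first 3 days in the placebo group", taken from a published study as "mean 275 mg SD 75 mg".
- **F2 (recording of outcomes).** "The cumulative intravenous opioid requirement at 24, 48, and 72 hour will be recorded". After the oral switch, "The cumulative breakthrough intravenous opioid requirement after initiation of oral pain medication will also be collected". After that, "Upon discharge from the hospital, the patients will be asked to keep a diary consisting of daily opioid usage".
- **F2 (postoperative analgesia).** PCA morphine is the only postoperative opioid named before POD 3. Scheduled oral hydrocodone with acetaminophen starts on POD 3, and the PCA stays available for breakthrough pain.
- **H1 (risks).** The aim is described in terms of all opioid used during the hospital stay.
- **Section K.** Medication information from health records is among the research data.

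**The concern.** A trial with a single primary endpoint needs one definition of it. Here two sections each name a primary endpoint, and the two are different variables. No section ranks them, makes them co-primary or marks one as superseded.

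Three things are at stake:

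- **Error rate.** The 5% level applies to one endpoint fixed in advance. It would not hold if the choice between two were left until results were known.
- **Power.** The planning mean and SD are for about three days. None is given for POD 0-4.
- **Interpretation.** A 72-hour morphine total and a five-day total of all opioids give different effect estimates, and the second needs a conversion between drugs.

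**Working it through.** **1. The definitions side by side**

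| Place | Window | Drugs |
|---|---|---|
| Section D | POD 0-4 (five calendar days) | all opioids |
| G2 | first 72 postoperative hours | morphine |
| G1 | first 3 days | opioids |
| F2, recording | 24, 48 and 72 h, then breakthrough after the oral switch | intravenous opioids |
| H1 | hospital stay | all opioids |

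On window, G1 and the timed F2 recording agree with G2, and Section D stands apart. On drugs, Section D, G1 and H1 all speak of opioids, and G2 is the narrow one. The drug difference matters mainly from POD 3. Within 72 hours, morphine and all opioids diverge only if oral dosing on POD 3 begins before hour 72. That can happen, because POD 3 is a calendar day and time zero for the 72 hours is not defined.

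**2. Data for the POD 0-4 total**

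F2 lists timed intravenous opioid, intravenous breakthrough opioid after the switch, and a diary after discharge. It does not list oral opioid given in hospital, and no section gives a conversion to morphine equivalents. Section K does bring medication records into the research data, so the oral doses can be obtained.

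**3. Power basis**

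G1's inputs are a difference of 275 - 200 = 75 mg, SD 75 mg, 80% power and alpha 0.05 (taken as two-sided). The normal approximation gives n = 2 × (1.960 + 0.842)² × (75/75)² = 15.7, so 16 per group; the t-test version gives 17. The stated 28 is not reproduced, and at 28 per group power is about 96%. That is a separate matter and the present point does not depend on it.

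For POD 0-4 the documents give no mean or SD. As an assumption-only illustration, keep the 75 mg difference and 28 per group and let the SD vary (t-test):

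| Assumed SD | Power at 28 per group |
|---|---|
| 75 mg | 96% |
| 100 mg | 79% |
| 125 mg | 60% |
| 150 mg | 45% |

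**4. Error rate if the version were chosen after results were seen**

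Assume no treatment effect, daily totals of equal variance, and a common correlation c between days within a patient. Treat the 72-hour total as 3 of the 5 days. The correlation between the two totals is then

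r = (3 + 12c) / √[(3 + 6c)(5 + 20c)].

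The chance that at least one total reaches two-sided p < 0.05 is 1 - P(|Z1| < 1.96 and |Z2| < 1.96), for a bivariate normal pair with correlation r.

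| c | r | False-positive rate |
|---|---|---|
| 0 | 3/√(3 × 5) = 0.775 | 7.96% |
| 0.3 | 6.6/√(4.8 × 11) = 0.908 | 6.95% |
| 0.5 | 9/√(6 × 15) = 0.949 | 6.48% |
| 0.7 | 11.4/√(7.2 × 19) = 0.975 | 6.0% |
| 0.9 | 13.8/√(8.4 × 23) = 0.993 | 5.6% |

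Simulated t-tests with 28 per arm (200,000 trials) gave 7.9%, 7.0% and 6.5% at r = 0.775, 0.91 and 0.95. As a check on the equal-variance assumption, suppose the part after 72 hours had the same SD as the first 72 hours and were uncorrelated with it. Then r = 0.71 and the rate is 8.3%.

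**The case against.** The strongest reply is that the plan already points to 72 hours. G2 answers the direct question about the primary analysis, G1 is sized on three days, and F2 records at 24, 48 and 72 hours. This stands as far as it goes. A reader might infer that the plan gives no clue which result is primary, and the documents do not support that on window. They still leave the contradiction in place: Section D is the formal statement of objectives, nothing subordinates it to G2, and the drug scope is not settled by the same evidence.

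A second reply concerns data. A reader might infer from F2 that the POD 0-4 total cannot be computed. Section K does not allow that reading, because medication records are available to the study. The total is under-specified, not out of reach.

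A third reply is that the error inflation is modest and rests on assumptions. This also stands. The 8% end needs no correlation between a patient's days, which is unlikely for totals in mg when doses are weight-based. The model also counts POD 0 as a full day and ignores that the later days are largely scheduled hydrocodone. A reader might infer that the investigators mean to choose after seeing results; nothing in the documents shows this.

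Time zero is a lesser matter. The PCA starts in the PACU on emergence, so reasonable choices would move the cut-off only slightly.

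**Conclusion.** The point holds and must be fixed, on the strength of the textual contradiction alone. Sections D and G2 name different primary endpoints, and no section reconciles them. Section D is the outlier on window and its version has no stated power basis; G2 is the narrower text on drug scope. The POD 0-4 total also lacks a listed source for in-hospital oral opioid and a conversion rule.

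The size is conditional. Choosing the version after seeing results would give a false-positive rate of roughly 5.5% to 8% instead of 5%, for an assumed correlation between the totals of about 0.99 down to 0.77. The documents do not give that correlation. With one endpoint fixed in advance the rate is 5% and no alpha adjustment is needed.

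A reader might also infer that intravenous morphine alone must be the primary. The documents do not settle this: G2 says morphine without naming a route, and G1 and H1 speak of opioids.

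**What to change.** Before unblinding, state one primary endpoint in the same words in Sections D, G1 and G2, with one window, a defined time zero and one drug scope.

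- **Window.** Aligning Section D to 72 hours is the smallest change, because the sizing and the timed recording already use it.
- **Drug scope.** The investigators should choose in advance between morphine only and all opioids in morphine equivalents, the latter by one prespecified conversion.
- **Planning values.** G1 should confirm that the 275 mg mean and 75 mg SD refer to the endpoint chosen.
- **POD 0-4 total.** Keep it as a secondary endpoint, with in-hospital oral doses taken from the medication record and the same prespecified conversion.

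The cost is wording in three sections and a little chart extraction, with no extra patients. The drawbacks are that any all-opioid total relies on a conversion factor, and that a 72-hour primary leaves most of POD 3-4 to the secondary endpoint.
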